1. SUMMARY

This is a 5-week, single-blinded, randomized trial to pilot test the efficacy of a behavioral intervention (CARE RA), a peer coach program, in increasing cardiovascular disease (CVD) risk assessment and self-efficacy in patients with rheumatoid arthritis (RA). Peer coaches are patients who themselves have the targeted condition (e.g., diabetes, RA) and have been trained to help others with the same condition in following treatment recommendations from their providers, social support, and improving self-efficacy, which translates into healthy behaviors. They are not physicians, nor other health professionals, and do not provide any medical advice to the patients they are coaching. We will explore their potential role to guide other patients with RA to obtain adequate CVD risk assessment, the most common cause of death in patients with RA.

The study population will consist of individuals with RA between the ages of 40-75 who have no history of established CVD and are not receiving a statin. The study duration will be 18 weeks, including a 6-week intervention period, starting from baseline enrollment and ending with the 3-month follow-up contact. Eligible subjects will be randomized to either a self-administered online learning arm or to the CARE RA arm, also called the peer coach arm. The self-administered online learning arm will include a tutorial on how to use the Patient Activated Learning System (PALS) followed by self-driven completion of the CARE RA curriculum within the PALS. The peer coach arm will include the same tutorial on the use of the PALS but will also include contacts with a peer coach for 5 weeks to reinforce key points in the CARE RA curriculum within the PALS. Each week, the peer coaches will have a 30 to 45-minute call with their assigned participant(s) during which they will discuss concepts about RA, CVD and RA, the importance of cardiovascular risk assessment, how to better communicate with your doctors, and how to request cardiovascular risk assessment from your doctor.

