3. STUDY OBJECTIVES AND OUTCOMES

3.1 Primary Objective

The primary objective is to test the difference in the proportion of subjects who receive cardiovascular risk assessment or learning from their healthcare provider that they already had one in the past year, between subjects randomized to the peer coaching condition and subjects randomized to the self-administered online learning condition.

3.2 Secondary objectives:

To determine whether the CARE RA program is effective in improving the following patient generated health data compared to subjects in the self-administered online learning arm.

1. Change in Routine Assessment of Patient Index Data (RAPID3) score from baseline to the end of the study between arms.
2. Change in Social Support Survey Score from baseline to the end of the study between arms.
3. Change in Patient Activation Measure (PAM) score from baseline to the end of the study between arms.
4. Change in Patient Health Questionnaire – 8 (PHQ-8) score from baseline to the end of the study between arms. Subjects who score a 10 or higher on the PHQ-8 at baseline data collection will be referred to mental health resources and counseling (websites, links, educational materials) by the study team. Peer coaches will be trained to direct subjects who express depressed thoughts and feelings during the course of the program to the mental health resources and counseling and will report such instances to the research team.
5. Change in General Self-Efficacy (GSF) score from baseline to the end of the study between arms.
6. Change in Medication Understanding and Use Self-Efficacy Scale (MUSE) score from baseline to the end of the study between arms.
7. We will examine the feasibility of the intervention by having 80% or more of the subjects complete the intervention.

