Groups of 4-8 peer coaches will be scheduled for online training meetings. The peer coaches will be part of the research team that will be conducting this study and will be considered community member consultants. There will be a total of 7 group web conference training sessions via Zoom over 2 months. At the first meeting, peer coaches will be introduced to the CARE RA intervention schedule (Table 3). Over the course of training, the research team will review each chapter of the Peer Coaches' manual to teach the activities that the peer coach will need to complete throughout the intervention. Frequently asked questions (FAQs) are included that will help peer coaches manage various situations that may arise with their client.

During each online group training meeting, the following activities will occur:

- Review of learning materials on PALS
- Review of Peer Coach Manual (each week's session calls will be scripted in these manuals)
- Didactic training in motivational interviewing skills
- Practice of motivational interviewing skills

Group web conferences will be supplemented by 2 motivational interviewing (MI) training sessions on zoom with the PI and/or research assistant and only two coaches. During these smaller MI

sessions, peer coaches will practice MI skills with reinforcement by the PI and/or research assistant. During each MI training session, the following activities will occur:

- Practice of motivational interviewing skills by each peer coach, using role-play scripts and alternating roles between coach and subject under the supervision of the PI and/or the research assistants of the study
- Reinforcement of skills in real-time with encouragement of peer coaches to critique each other's skills

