Group training sessions will be accompanied by paired practice sessions. Each coach will be paired with another coach. They will be asked to listen to the PI and/or research assistant delivering each session to a mock subject on audio recordings. They will then each practice delivering the intervention session in turn to their partner. Each coach in training will be encouraged to critique their partner's performance based on MI skills learned earlier in training. If coaches do not feel confident that they have mastered a session, they will be encouraged to continue to practice with their partner. Once each coach feels confident, they will schedule a separate one-on-one certification session with the PI and/or research assistant. At this session the PI and/or research assistant will play the role of the subject and the coach will deliver the session. The PI and/or research assistant will use a checklist to assess proficiency. Each coach will be certified on each session separately. If needed, additional training can be scheduled until each coach reaches the minimum level of proficiency. Only those that pass all the certification sessions will be allowed to work with subjects in the study.

Peer Coach Retention

Retention activities consist of the following:

- Ensure timely payment for work
- Provide ongoing support and continuing education/retraining with opportunities for practicing skills
 - Weekly group conference calls to assess process measures and monitor progress of the intervention
 - Provide group problem-solving for challenges encountered
 - Provide emotional support
 - Build group identity and pride
- Allowing each coach to determine their workload, increasing or decreasing according to life demands
- Be respectful of peer coaches' time and schedules
 - Keep mandatory conference calls and individual calls on time, short as possible, and reschedule only if necessary.
 - Provide assistance as needed in scheduling sessions with subjects

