5.4 Recruitment

Figure 2 outlines the workflow of this study from recruitment to final data collection.

Recruitment

We will send out invitations to participate in CARE RA to members of the ArthritisPower registry and the Bendcare patient network via email messages in several waves. We will send out 200-400 invitations at a time and continue to send out invitations based on the response and on peer coach capacity. Bendcare will also reach out to their patients to determine their interest in this study. Bendcare will screen patients for eligibility. Eligible patients will be consented by Bendcare and transferred to the research team for randomization. Bendcare will provide access to this REDCap database used to screen and consent Bendcare patients to the WCM research team within their secure network. We will also be recruiting participants using flyers created by a company (BuildClinical). These flyers will be posted online and interested participants will be referred to us. If the patient clicks on the online flyer, they'll be prompted to complete the BuildClinical screening survey based on our eligibility criteria.

We will post a recruitment video on Twitter through the PI's professional account. The recruitment video will briefly detail the CARE RA study and invite people to fill out an interest survey through REDCap if they would like to be contacted by the research team for more information. Once an individual completes the interest survey, the research team will reach out to them.

We will further increase recruitment through the patient list of [name], [name], [name], [name], [name], and [name]. All physicians have provided our team with authorization to contact their patients whom our team will identify using EPIC. To help streamline the process of identifying patients, we will use the EHR Data and Reporting system TRAC to extrapolate patients that meet the eligibility criteria. We will not reach out to patients who marked in EPIC their wish not to be contacted for research. We will reach out to patients through doximity.

Once a person consented to participate in the study, all data collected will follow those stipulated by the study. These recruitment processes will be in place until 128 subjects are recruited.

Screening

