We will use REDCap to collect the data at baseline, post-intervention, and final follow up. The subject will receive a REDCap link via email that they will click to access the surveys at each data collection point. A blinded research assistant from WCM will follow up by phone with those subjects that have not completed or partially completed the surveys to minimize missing data.

Session	Objectives	Activity/Assignment	PALS - Renewable Knowledge Objects (RKOs)
1. "Introduction to the CARE RA Program"	
 1. Get to know each other 2. Introduce the CArteriovascular Risk assEssment Program for Rheumatoid Arthritis (CARE RA) program 3. Introduce the client to the Patient Activated Learning System (PALS) 	
 A. Verify contact information and receipt of Activity Book B. Get to know each other C. Introduce the CARE RA program D. Introduce the PALS E. Rules and Responsibilities F. Sign contract G. PALS assignments (RKOs) for Session 2 H. Schedule Session 2 call 	None for Session 1
2. "RA and My Heart"	
 1. Learn how RA affects your heart 2. Learn why a cholesterol test is needed to assess risk for heart attack and stroke 	
 A. Greetings between coaches and clients B. Verify the client has reviewed the RKOs and introduction to Session 2 C. Review of PALS assignments for Session 2 D. CARE RA Highlights of Session 2 E. Plans for Session 3 F. PALS assignments for Session 3 G. Schedule Session 3 call 	
Required:
 
 - How can rheumatoid arthritis (RA) affect my body and my health? - What does atherosclerotic cardiovascular disease (ASCVD) risk mean? - How does rheumatoid arthritis (RA) affect my heart? - How can I lower my risk of heart disease if I have rheumatoid arthritis (RA)? - What is cholesterol? - Do I need a cholesterol test if I have rheumatoid arthritis (RA)? 
Learn more:
 
 - What is rheumatoid arthritis (RA)? - How is rheumatoid arthritis (RA) treated? - What medicines are used to treat rheumatoid arthritis (RA)?

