8.2 Data Analysis

To analyze the data, descriptive analyses (means, medians, standard deviations, proportions, and frequency distributions) and correlation analyses (Spearman/Pearson rank correlations) will be conducted to assess and describe the cohort. Baseline comparability between study arms will be assessed with parametric and nonparametric analyses including two sample t-tests, Wilcoxon Rank Sum, and Chi-Square tests of proportions. Every effort will be made to keep subjects in the study for the entire follow-up. Analysis will be based on intention-to-treat, regardless of whether the subject completed the intervention program. The primary outcome is the percentage of patients with lipids checked (available now through national laboratory chain) or that reported having their lipids checked. Secondary outcomes include the percentage of subjects that reported initiating LLT, self-efficacy, and patient activation as described above. We will determine these outcomes in each group (self-administered online learning program and the CARE RA arm) as well as differences in these outcomes between the groups. Two-sided t-tests will be used to calculate differences and P values ≤ 0.05 will be considered statistically significant. We will examine differences in socio-demographics, disease severity, and depressive symptoms. These characteristics will be included in a multivariable logistic regression model to determine their association with the outcome (lipids being checked) and potentially increase the statistical power of the test of group differences.

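### The six survey scores have no baseline-adjusted analysis although baseline is collected, and section 8.2 has no sensitivity analysis for CARE RA subjects who share a peer coach

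*Combined protocol and SAP*

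**What the plan says.** **Endpoints.** Sections 1 and 3.2 give all six scores (RAPID3, Social Support Survey, PAM, PHQ-8, GSF, MUSE) the same form, for example "Change in Social Support Survey Score from baseline to the end of the study between arms".

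**Analysis.** Section 8.2 names self-efficacy and patient activation as secondary outcomes, refers back to the earlier description, and states: "Two-sided t-tests will be used to calculate differences and P values ≤ 0.05 will be considered statistically significant". It does not say whether the tests are on change or on the final score; change is the natural reading given section 3.2. Its only adjusted model is a multivariable logistic regression for lipids checked.

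**Data.** Section 7.2: "We will use REDCap to collect the data at baseline, post-intervention, and final follow up". Table 2 lists all six scores at baseline, about one week after the intervention, and three months after it.

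**Order of events.** In section 5.4 the subject is randomised, is told the arm by phone, and in the same call is shown how to complete the baseline form, which arrives by email.

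**Coaches.**
- Section 1 leaves the plural open: each week "the peer coaches will have a 30 to 45-minute call with their assigned participant(s".
- Section 4.2 lists among its retention measures "Allowing each coach to determine their workload, increasing or decreasing according to life demands".
- Section 5.4 says the team will "continue to send out invitations based on the response and on peer coach capacity".
- Section 7.1 has each coach report on several clients.
- Section 4.2 gives the size of a training group ("Groups of 4-8 peer coaches will be scheduled for online training meetings"), but no section gives the total number of coaches, a caseload or an ICC.
- Neither 8.1 nor 8.2 mentions coach.

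**The concern.** Two gaps in section 8.2 affect how accurately uncertainty is stated.

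The first is lost precision. A change score subtracts the whole baseline value, whereas regression on baseline subtracts only the part that predicts follow-up. Section 8.2 accepts covariate adjustment as a way to gain power for lipids checked, but does not apply it to the scores, whose own baseline is an obvious covariate.

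The second is the independence assumption. Control subjects have no coach. CARE RA subjects who share one may have correlated outcomes if some coaches are more effective than others. Sections 8.1 and 9 look ahead to a more definitive trial and an expanded program, so readers will want the result to hold for other coaches. For that purpose ordinary standard errors are too small if effects vary by coach. This touches lipids checked, the primary outcome in 8.2, as well as the scores.

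**Working it through.** **1. Inputs.** From the documents: 64 subjects per arm (8.1), two-sided 0.05 (8.2), individual randomisation with matching to a coach afterwards (5.4). Assumed, because the documents are silent: baseline to follow-up correlation rho, number of coaches, ICC.

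**2. The plan's own figure.** For 80% against 60%, one-sided 0.05, 80% power, pooled variance:

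n = [1.645·√(2·0.7·0.3) + 0.842·√(0.16 + 0.24)]² / 0.20² = 63.9, so 64 per arm.

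The figure reproduces with all subjects treated as independent. The rest of the check uses two-sided 0.05, as in 8.2.

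**3. Precision.** With SD s at both times, the outcome variance that enters the comparison is 2s²(1 − rho) for change and s²(1 − rho²) for ANCOVA. The ratio is (1 + rho)/2. The detectable difference in SD units (64 per arm, 80% power) is 2.80·√(2/64 · relative variance).

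| rho | Variance ratio | SE ratio | Detectable, change | Detectable, ANCOVA |
|---|---|---|---|---|
| 0.5 | 0.75 | 0.866 | 0.495 | 0.429 |
| 0.7 | 0.85 | 0.922 | 0.384 | 0.354 |
| 0.8 | 0.90 | 0.949 | 0.313 | 0.297 |

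**4. Baseline reported after the arm is known.** Suppose knowledge of the arm shifts reported baseline in one arm by d. Relative to the difference in follow-up score, the change-score comparison is off by d and ANCOVA by rho·d. With d = 0.2 SD and rho = 0.5 (both assumed), that is 0.20 SD against 0.5 × 0.2 = 0.10 SD. ANCOVA is less exposed, but not immune.

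**5. Shared coaches.** One-to-one coaching of 64 subjects would need 64 certified coaches, that is 64/8 = 8 to 64/4 = 16 training groups. Nothing in the documents suggests this. With m subjects per coach, the CARE RA variance is multiplied by DE = 1 + (m − 1)·ICC and the control variance is unchanged. The SE is therefore understated by r = √[(1 + DE)/2], and the true two-sided error is 2·[1 − Φ(1.96/r)].

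| Coaches (m) | ICC 0.01 | ICC 0.05 | ICC 0.10 |
|---|---|---|---|
| 32 (2) | 5.1% | 5.3% | 5.6% |
| 16 (4) | 5.2% | 5.9% | 6.8% |
| 8 (8) | 5.4% | 7.1% | 9.2% |

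For 8 coaches at ICC 0.05: DE = 1.35, r = √1.175 = 1.084, 1.96/1.084 = 1.808, error 7.1%.

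For uneven caseloads, replace m by Σm²/Σm. With 16, 12, 10, 8, 6, 5, 4 and 3 subjects this is 650/64 = 10.16, which gives 7.7% at ICC 0.05 and about 10% at 0.10. Simulated error for lipids checked (60% in both arms, equal caseloads) is 5.9% (16 coaches, 0.05), 7.1% (8, 0.05) and 9.0% (8, 0.10).

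These figures take coach effects as varying around zero and the coaches as a sample from a wider pool. If coaching affects no one, simulation gives 4.9%, even when matching by prognosis produces an apparent coach ICC of 0.30.

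**6. How the proposed sensitivity analysis behaves.** This is CR2 standard errors with Satterthwaite df, simulated with 128 subjects and rho 0.5:
- Equal caseloads: error 4.7% to 5.4% over ICC 0 to 0.10.
- Uneven caseload above: up to 5.9% for scores and 6.1% for lipids checked.
- Interval width against ordinary ANCOVA: 2% wider (32 coaches, 0.05), 5% (16, 0.05), and 3%, 12% or 20% (8 coaches at ICC 0, 0.05 or 0.10). For the uneven caseload it is 5% wider at ICC 0 and 15% at 0.05.
- If similarity within a coach comes only from matching (8 coaches, apparent ICC 0.05): error 3.6%, which is conservative.

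**The case against.** *On baseline.* A change score already uses the baseline, these are secondary outcomes of a declared pilot, and an SE reduction of 5% to 13% is modest. That is fair, and it limits the weight of the point. A reader might go further and infer that the change-score t-test is biased. Randomisation does not support that: both analyses are unbiased provided baseline is reported independently of the arm. The order of events in section 5.4 weakens that proviso, so neither can be called a matter of precision alone, but the weakness does not favour the change score.

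*On coaches.* The inflation needs three things that the documents do not supply: a coach count, an ICC, and an explicit wish to extend this trial's p-values to other coaches. Scripting ("session calls will be scripted in these manuals"), certification of each coach on each session, and review of recorded sessions may keep coaches alike. All of this stands. A reader might infer that shared coaches invalidate the primary test, or that the 128 must be increased. Neither follows. Subjects are randomised individually and matched afterwards, so the test keeps about 5% if coaching affects no one, and there is no documented ICC from which to recalculate a sample size. Nor can 4 to 8 be read as the total number of coaches: it is the size of one training group, and the text speaks of groups in the plural.

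The coach-adjusted analysis also has limits of its own (step 6), so it should not replace the main one.

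**Conclusion.** The omission of a baseline-adjusted model is clear from the text. Its cost is 10% to 25% of variance for rho of 0.8 down to 0.5, assuming equal SDs at baseline and follow-up. Correcting it is a free improvement, and it holds with the caveat about when baseline is reported.

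The omission of any allowance for coach is equally clear, but its consequence is not. It ranges from negligible (many coaches, low ICC, or interest only in these coaches) to material (about 8 coaches, ICC 0.05 or more, and a result meant to generalise). That justifies a cheap prespecified sensitivity analysis and no more.

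**What to change.** **1. Section 8.2, scores.** Replace the t-tests by ANCOVA for each score: score at a named follow-up on arm and baseline score. State which visit is the end of the study. If it is the three-month contact, make that the main comparison and report the one-week score in the same way; a repeated-measures mixed model with baseline as covariate could give both. Cost: wording only.

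**2. Section 5.4, order.** Have the baseline form completed before the arm is disclosed. If enrolment is too far advanced for this, report the order as a limitation. Cost: a change in the sequence of enrolment contacts.

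**3. Section 8.2, sensitivity analysis.** Keep in the analysis file the coach ID that the team already holds from matching. For the six scores, and for lipids checked on the risk-difference scale, report CR2 standard errors with Satterthwaite df. Cluster by coach in the CARE RA arm only, and enter control subjects and never-matched CARE RA subjects as singletons so that intention-to-treat is kept. Avoid the simpler CR1 correction with df from the total number of clusters, which leaves 6% to 8% with 8 coaches. Also avoid a test on coach means, which weights coaches rather than subjects. State the limits in the plan: wider intervals, error still up to about 6% with uneven caseloads, and conservatism if similarity comes only from matching. Report the coach ICC with its interval as descriptive only, since it will be imprecise. Cost: one variable, a paragraph of SAP text and a little more analysis; no new subjects, visits or instruments.

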	
 -How many subjects in the CARE RA arm received a cholesterol test during the program compared to the control arm? -How many subjects in the CARE RA arm received a cholesterol test by 1-week post intervention follow up compared to the control arm? -How many subjects in the CARE RA arm received a cholesterol test by 3-months post intervention follow up compared to the control arm? -How many subjects in the CARE RA arm initiated a statin, if indicated, after completion of the program in each arm? - See statistical analysis section for details. -How many subjects saw an improvement in their secondary outcomes (RAPID3, SSS, PHQ-8, PAM, MUSE, and GSE) from baseline to 1-week and 3-month post intervention data collection between arms? -Were you able to understand the program information? -Do you believe the program information is valuable to living a healthy life?
ADOPTION	Organization Level
	
 -What factors contributed to ArthritisPower and its members, and the Bendcare network, to taking up the intervention? -What barriers interacted with the intervention to prevent adoption within ArthritisPower and the Bendcare patient network? 
ADOPTION will be assessed upon completion of the trial through talking with members of the ArthritisPower community and the Bendcare patient network.

IMPLEMENTATION **Individual Level**

- To what extent were the intervention components delivered as intended in the protocol?
- How was the intervention implemented? By whom and when?
- How was the program adapted or modified over time?
- What was it like to deliver this program to individuals with rheumatoid arthritis?
- What do you think was most successful? What were the major barriers in implementing this program?
- What was it like to conduct the weekly sessions?
- Would you do anything to revise the program?
- Does the program improve my ability to deal with life's challenges to my health?
- Does using the program makes it easier to live a healthier life?
- Is the program useful in my life?
- How satisfied are you with the program?
- Was participating in the program difficult for you?
- Would you recommend the program to people you know?

This dimension will be assessed through surveys and focus groups/interviews with the subjects.

MAINTENANCE **Organizational and Individual Level**

- What was the attrition rate; were drop-outs representative of the target population?

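### Six secondary survey scores are each open to an effectiveness claim at an unadjusted two-sided 0.05, with no gate on the primary result and no exploratory label

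*Combined protocol and SAP*

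**What the plan says.** Section 3.2 introduces the patient-reported scores with an effectiveness aim: "To determine whether the CARE RA program is effective in improving the following patient generated health data". Six scores follow, each as a single change, for example "Change in Routine Assessment of Patient Index Data (RAPID3) score from baseline to the end of the study between arms". A seventh item is an 80% completion target for feasibility, which is not a comparison between arms.

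Section 8.2 names one primary outcome, lipids checked. It then adds: "Secondary outcomes include the percentage of subjects that reported initiating LLT, self-efficacy, and patient activation as described above". It says these outcomes will be compared between groups and gives the rule: "Two-sided t-tests will be used to calculate differences and P values ≤ 0.05 will be considered statistically significant". No other significance rule for the secondary outcomes appears in the documents.

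Two other places matter. Under Effectiveness, Table 4 in section 9 asks about improvement in all six scores "from baseline to 1-week and 3-month post intervention data collection between arms". The Summary states the aim of the trial as efficacy "in increasing cardiovascular disease (CVD) risk assessment and self-efficacy in patients with rheumatoid arthritis (RA"; two of the six scales, GSF and MUSE, measure self-efficacy.

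**The concern.** The 3.2 objective and the 8.2 rule together determine what the trial may report. A score with P ≤ 0.05 is statistically significant by the plan's own rule, and it answers an objective worded as a test of effectiveness. Nothing makes that reading depend on the primary result. With six scores, an ineffective program has six chances to yield such a result, and the plan would allow it to be reported as an effect even if the proportion with lipids checked did not differ. Section 8.1 says the data will be used to design a more definitive trial, so a chance finding on one scale could be carried forward as if established.

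**Working it through.** **The plan's own figure.** The documents state a per-test level of 0.05 and no familywise error rate, so there is no plan figure to reproduce for this point. The one derived figure in section 8 does reproduce: 80% against 60%, one-sided 0.05, gives 64 per group with power 80.1%. It concerns the primary outcome only.

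**Inputs.**
- Number of scores k = 6 (section 3.2).
- Level 0.05 two-sided (section 8.2), so c = 1.96 and 0.025 in each direction.
- One time point, the end of the study (section 3.2).
- Correlation ρ between the six test statistics: not in the documents. Assumed common to all pairs, with scores oriented so that positive means benefit; range 0 to 0.8.

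**Independent scores (ρ = 0).**
- Any false significant score: 1 − 0.95^6 = 0.265.
- At least one favouring CARE RA: 1 − 0.975^6 = 0.141.

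**Correlated scores.** With a common correlation ρ, and φ and Φ the standard normal density and distribution function:
- Any direction: 1 − ∫ φ(u) [Φ((c − √ρ·u)/√(1−ρ)) − Φ((−c − √ρ·u)/√(1−ρ))]^6 du.
- Favouring CARE RA: 1 − ∫ φ(u) [Φ((c − √ρ·u)/√(1−ρ))]^6 du.

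| ρ | Any direction | Favouring CARE RA |
|---|---|---|
| 0 | 26.5% | 14.1% |
| 0.3 | 24.1% | 12.2% |
| 0.5 | 20.7% | 10.4% |
| 0.7 | 16.4% | 8.2% |
| 0.8 | 13.9% | 6.9% |
| Single test | 5% | 2.5% |

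Simulation under the same assumptions agrees to within about 0.1 percentage point.

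**Sensitivity to the number of tests.**
- *Narrow reading of 8.2.* Suppose the rule reached only the scores that 8.2 names, self-efficacy (GSF and MUSE) and activation (PAM). Then k = 3 and ρ = 0 give 1 − 0.95^3 = 14.3% in any direction and 1 − 0.975^3 = 7.3% in favour.
- *LLT initiation added.* k = 7 gives 30.2% in any direction at ρ = 0 and 23.0% at ρ = 0.5.
- *Both follow-up contacts tested.* Six scores at two times, k = 12, give 31.9% in any direction and 16.0% in favour at a common correlation of 0.5; at ρ = 0 they give 46.0% and 26.2%.

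**The case against.** The strongest reply is that this is a pilot with one designated primary outcome, that the six scales measure different constructs, and that leaving the secondary outcomes of a pilot unadjusted is common. Part of this stands. The plan does rank one outcome above the others, so it would be wrong to say it has no hierarchy; what it lacks is a gate from the primary to the secondaries and any order among the secondaries. The plan also never claims 5% familywise control, and section 8.1 says the next trial will be powered on the primary outcome, which limits the harm.

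The pilot label does not settle the matter. Section 8.1 uses it to explain the modest sample; it does not withdraw the significance rule or the effectiveness wording. A pilot meant only to estimate effects would need neither for its secondary outcomes.

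Three stronger readings are tempting, and the documents do not support them.
- *A 20% to 35% chance of a false efficacy claim.* Rates of that size count significance in either direction, and a result favouring control cannot support the program. The upper end also needs about 14 tests: six scores plus LLT initiation, at both contacts. Section 8.2 does not prespecify these, section 3.2 gives one change per score, and Table 4 sets no test or threshold of its own. Seven tests at one time point cannot exceed 30.2% when independent or positively correlated.
- *LLT initiation is covered by the effectiveness objective.* The list in 3.2 does not contain it. Section 8.1 counts it in the primary outcome while 8.2 calls it secondary, a separate conflict.
- *Self-efficacy must leave the Summary's aim.* Multiplicity does not require that; section 4.4 gives activation and self-efficacy as the intervention's goal.

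**Conclusion.** The point holds for the six scores. As written, the plan lets a single unadjusted P ≤ 0.05 on any of them count towards effectiveness, whatever the primary shows. At one time point the chance of at least one false significant score is about 21% (14% to 26%), and of one favouring CARE RA about 10% (7% to 14%): roughly four times the single-test rates of 5% and 2.5% at a correlation of 0.5.

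These sizes assume no effect on any score, approximately normal test statistics and a common non-negative correlation that the documents do not give. The direction of the conclusion does not depend on the correlation: even at 0.8 both rates are well over twice the single-test rate. For a pilot this is a modest defect, but it changes what the trial may conclude and is cheap to correct.

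**What to change.** 1. In 8.2, limit the P ≤ 0.05 rule to the single primary comparison.
2. In 8.2, state that the six scores, and any secondary analysis of LLT initiation, are exploratory, are reported as between-arm differences with 95% confidence intervals, and support no effectiveness claim on their own.
3. Confirm the 3-month contact as the end of the study for each score (section 5.2 counts the 3 months from enrollment, Table 2 from completion of the intervention). Treat the 1-week scores and the Table 4 counts of improvers as descriptive.
4. In 3.2, replace "To determine whether the CARE RA program is effective in improving the following patient generated health data" with an estimation aim that opens *To estimate the effect of the CARE RA program on* the same scores. Self-efficacy can stay in the Summary as an aim to be estimated.

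This needs no new data, contacts or subjects. The cost is that one scale with P ≤ 0.05 can no longer be called a significant effect.

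If the sponsor wants to keep claims on the scores, Holm's procedure across the six 3-month scores, after a significant primary, is an alternative with a real price. The first step needs P ≤ 0.05/6 = 0.0083. With 64 per arm, this cuts power for an illustrative 0.5 SD difference from about 80% to 56%. The gate lowers it further: two-sided power for the primary at 64 per group is 69.9%, so if the tests were independent the joint chance would be 0.699 × 0.560 = 39%.
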